### Statistical analysis

Descriptive statistics will be reported for each group. Means with standard deviation and 95% confidence intervals of the means will be reported for continuous variables and frequency and proportion distribution will be reported for categorical outcomes.

Student t-test (for normally distributed continuous variables) and Wilcoxon rank sum tests (for non-normally distributed variables) will be used to compare continuous outcomes such as AUC for adult NVPS/ NRS and opioid requirements between the two groups. For categorical outcomes, chi-square tests will be used to compare differences between the two groups. If some cell counts are small and the asymptotic tests are not reliable, then exact methods will be used. A general linear regression model for NRS scores will be applied to show the main effect for the treatment group, adjusting for covariates. Regression analysis will also be applied to opioid requirements. For the binary outcome of whether a patient has reached his/her maximum allowed dose of opioid, logistic regression models will be applied. For the opioid requirement outcome, patients who have reached their maximum allowed dose of opioid will be treated as censored and a Tobit regression model will be applied. Since there are two primary outcomes, a type I error of 2.5% will be used. All the tests will be two-sided.

Survival analyses will be applied for time to event data, such as the lengths of stay and mean time to return of bowel function. Logrank tests will be applied for simple comparisons between the two groups. Cox proportional hazards models will be used to facilitate the inclusion of covariates in the regression analysis. Note that although no censoring of subjects are expected in the study (i.e. the lengths of stay and mean time to return of bowel function will be observed for each patient) and a general linear regression analysis may be applicable, our survival analysis approach enables us to estimate the survival curves and read the different rates at different time points from the curves.

Since variables such as NRS are measured repeatedly over the 72-hr time period, we may refine our analysis by using all of the measures instead of using the simple summarizing index, AUC. Methods for longitudinal data will be applied to deal with the correlation among repeated measures in the same patient. The two most popular approaches for longitudinal data modeling are the generalized estimating equations (GEE) approach and the mixed-effects model (MM) approach. MM explicitly models between- and within-subject variation using random effects, and thus has the advantage of being able to separate between-subject variability from the total variability of responses. However, it requires parametric assumptions on observed and latent variables, which render inference vulnerable to departures from a normal distribution. An alternative approach to these models is the GEE approach. GEE ignores between-subject variability in model specification, but accounts for such variability during model estimation in order to ensure inference validity; therefore, GEE can provide robust estimates for between-group differences, as it does not require any assumption of the distribution. However, GEE is limited in that it requires the missing completely at random (MCAR) assumption, which may be violated. We will examine the nature of the missing data and use a weighted GEE (WGEE) approach as needed to address potential informative dropout. Our hypotheses concern between-group differences, so both parametric and semi-parametric approaches will be used. Both approaches will be used in the analysis and if discrepancies in MM and GEE (or WGEE) analyses occur, GEE (or WGEE) will be recommended, as the latter semi-parametric approach generally provides more robust inference.

All analyses will be performed using the latest version of SAS, which includes procedures for all of the analyses proposed, including Tobit regression, survival analysis, linear mixed model, and GEE (or WGEE) models. A statistician will be involved in reviewing the final analyses and confirming statistical soundness.

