**Figure 3.** Cross-sectional diagram of DepoFoam® drug delivery system containing aqueous chambers filled with Bupivacaine.

Reproduced from Chahar P, Cummings KC. *Liposomal bupivacaine: a review of a new bupivacaine formulation.* J Pain Research. 2012.

To compare differences in pain control, we will use a number of validated pain assessment tools. These include the adult nonverbal pain scale (NVPS), numerical rating scale (NRS) and brief pain inventory (BPI) (see Appendix II and III). The NVPS has been adopted by the cardiovascular ICU (CVICU) for assessing pain in critically-ill, intubated patients. It includes assessments of the patient’s face, body movements, muscle tension and vital signs to determine a total score ranging from 0 to 10. It has been shown to exhibit high reliability and inter-rater agreement, as well as increase patient and staff satisfaction. The NRS is an 11-point scale ranging from 0, “no pain”, to 10, “the worst possible pain”, that is used by nursing staff for

assessing and documenting pain in extubated, alert patients. The scale has shown high sensitivity and simplicity. Moreover it is interval and allows for parametric analysis. The BPI consists of four questions rating pain severity and seven questions regarding impact of pain on daily function, allowing calculation of pain severity and interference indices for comparison. Studies have shown that BPI scores correlate with the number of days from surgery and decreasing analgesic requirements.

Exparel® is not currently FDA-approved for peripheral nerve blocks. There are two ongoing clinical trials studying the use of Exparel® for femoral nerve blocks. However, Exparel® has not previously been studied for our specific application. Thus, we are conducting this study to evaluate the efficacy and safety of Exparel® in parasternal nerve blocks in cardiac surgery patients. Successful use of Exparel® for parasternal intercostal nerve blocks may revolutionize the management of post-cardiac surgery pain. Optimal pain control and reduced opioid doses would enable earlier extubation and mobilization, less opioid-associated morbidity and shorter ICU and total hospital lengths of stay.

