**Hypothesis:** We hypothesize that administration of Exparel® in parasternal nerve blocks will provide improved pain control and decreased narcotic use in the adult post-operative cardiac surgery patient.

**Primary aim:** To determine if there is a statistically significant improvement in analgesia and decreased opioid requirements in the post-operative period.

**Secondary aim:** To look at differences in LOS (ICU and hospital), time to return of bowel function, and time to return to work or daily activities. We will also look at incidence of complications related to inadequate pain control and the incidence of adverse events.

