## II. CHARACTERISTICS OF THE RESEARCH POPULATION

### Number of subjects.

The study will include 78 patients, 39 patients in the study drug arm and 39 patients in the control arm. Since there are two primary outcomes, we set the type I error at 0.025 for the power analysis. Based on results from a prior study by Barr et al., we assumed a baseline Numerical Rating Scale (NRS) score for pain of 53.2 with standard deviation of 24.1 and a baseline cumulative morphine requirement over 24 hours of 23.2 mg with standard deviation of 8.3 mg. The proposed sample size was calculated to achieve 86% power to detect a 30% decrease in mean NRS scores at the 2.5% level of type I error (two-sided). This sample size also provides for a 98% power to detect a 30% decrease in total opioid consumption over the first 24 hours post-operatively. Note that we assumed the standard deviation decreases accordingly. A 5% drop out rate was included into the sample size calculation.

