### Randomization and Blinding

Patients will be randomized on the day of surgery to either placebo or treatment group. The subjects will be randomized in blocks of 4 to ensure a 1:1 ratio of placebo to treatment groups.

- Placebo: 0.9% normal saline
- Treatment group: 0.53% Exparel®

A randomization sheet will be generated by the study pharmacist, listing the randomization schedule in sequence for each block. The study pharmacist will have control of the randomization sheet. At the time of randomization, he will go to the next available row to determine which medication to dispense. The randomization sheet will document each subject's number, initials, date of surgery and study arm (active or placebo).

The study pharmacist will hold the key identifying which study group corresponds with which letter. In order to maintain blinding of the study investigators, the pharmacist will not reveal the subject's group assignment and data collection will be done according to the subject number. At quarterly intervals during the trial, the study pharmacist will reveal the blinding to the Independent Data/Safety Monitor (DSM) only. This will enable the Independent DSM to capture for any alarming trends in adverse events or serious adverse events as they are occurring. At completion of data collection and analysis for the entire study, the pharmacist will provide the study investigators with a copy of the report revealing which subject belonged to which study group.

The subjects will be blinded to their study arm and remain blinded for the entire duration of this study. Subjects who wish to know which drug they received (Exparel® or placebo), may contact the PI or co-PI and they will be informed of their study group following completion the study.

The study investigators, surgeon administering the medications, operating room staff and ICU/floor staff will all remain blinded. Only the pharmacist who will prepare and dispense the medication will be unblinded.

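### Safety is a stated purpose, but the only planned comparison of adverse events is a chi-square or exact test; with 39 patients per arm, a risk difference with an interval is needed instead

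*Combined protocol and SAP*

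**What the plan says.** The Background section of the combined protocol and SAP gives the purpose as follows: "we are conducting this study to evaluate the efficacy and safety of Exparel" in parasternal blocks. It adds that the drug is not approved for peripheral nerve blocks and has not been studied in this use. The secondary aim continues: "We will also look at incidence of complications related to inadequate pain control and the incidence of adverse events".

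The events to be captured are listed under *Adverse events will be recorded*. Toxicity signs appear under *Cardiac and Neurologic Monitoring*, and nausea and vomiting in the Appendix I schedule. The *Data Analysis* list, which goes outcome by outcome, has no adverse event entry. Adverse events therefore fall under the general rule in *Statistical analysis*. For description, "frequency and proportion distribution will be reported for categorical outcomes". For comparison, "For categorical outcomes, chi-square tests will be used to compare differences between the two groups", with exact methods when cells are small, all two-sided. The 95% confidence intervals in that section are for means of continuous variables.

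On size, "The study will include 78 patients, 39 patients in the study drug arm and 39 patients in the control arm". The calculation uses pain and opioid consumption only: "Since there are two primary outcomes, we set the type I error at 0.025 for the power analysis". No power, precision or detectable difference is given for any adverse event.

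*Data Safety Monitoring Plan* adds unblinded independent review at 25, 50, 75 and 100% of enrollment and reporting of serious events to the monitor within 24 hours. *Indications for termination of study* describes stopping for excessive related serious events. Neither section gives a numeric bound.

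**The concern.** A reader who wants to know whether the block is safe asks how much excess risk the data rule out. A p-value on a handful of events does not answer that, and the plan provides no other comparative output. A non-significant result would be compatible with a large excess, and nothing in the planned report would show it. What is at stake is the safety statement of a trial that classes itself as greater than minimal risk. The two primary outcomes are not affected.

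**Working it through.** **The plan's own figures.** Inputs from *Number of subjects*: NRS mean 53.2, SD 24.1; opioid mean 23.2 mg, SD 8.3 mg; a 30% reduction, with the SD taken to fall in proportion; two-sided 2.5% (critical value 2.241); 39 per arm.
- NRS: difference 0.3 × 53.2 = 15.96. SD = √[(24.1² + 16.87²)/2] = 20.80. SE = 20.80 × √(2/39) = 4.71. Power = Φ(15.96/4.71 − 2.241) = 87.4%; with the t distribution, 86.2%; with 37 evaluable per arm (5% dropout), 85.5%. Stated: 86%.
- Opioid: difference 6.96 mg, SD 7.16, SE 1.62. Power = 98.0%. Stated: 98%.

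The efficacy figures reproduce. There is no safety figure to reproduce.

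**Power of the adverse event test.** I enumerated all 40 × 40 outcomes of two binomials with n = 39, placebo rate p and Exparel rate 2p. Two assumptions are mine. The plan does not define a small cell, so I used Pearson chi-square unless an expected count is below 5, and Fisher's exact test otherwise. The placebo rates are assumed, because the documents give none. The plan's 2.5% level is justified by the two primary outcomes and no level is named for adverse events, so both levels are shown.

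| Placebo → Exparel | Missed, 5%, 39 per arm | Missed, 5%, 37 per arm | Missed, 2.5%, 39 per arm |
|---|---|---|---|
| 5% → 10% | 95% | 96% | 98% |
| 10% → 20% | 78% | 80% | 86% |
| 15% → 30% | 64% | 66% | 74% |
| 20% → 40% | 50% | 53% | 63% |
| 30% → 60% | 22% | 26% | 30% |

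Hand check of the 10% → 20% row by the normal formula: null SE = √(2 × 0.15 × 0.85/39) = 0.0809; alternative SE = √[(0.10 × 0.90 + 0.20 × 0.80)/39] = 0.0801; power = Φ[(0.10 − 1.96 × 0.0809)/0.0801] = Φ(−0.73) = 23%, so 77% missed. Fisher throughout gives 84.5% missed and uncorrected Pearson 75.9%, so the choice of test does not change the picture.

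**What an interval would add**, with 39 per arm (Newcombe 95% intervals for Exparel minus placebo):

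| Events, Exparel v placebo | Fisher p | 95% interval, points |
|---|---|---|
| 5 v 0 | 0.055 | +1.3 to +26.7 |
| 4 v 2 | 0.67 | −8.2 to +19.0 |
| 8 v 4 | 0.35 | −6.2 to +26.5 |
| 2 v 2 | 1.00 | −12.3 to +12.3 |
| 0 v 0 | 1.00 | −9.0 to +9.0 |

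For 5 v 0, the Wilson limits are 5.6% to 26.7% and 0% to 9.0%. The lower limit is 0.128 − √[(0.128 − 0.056)² + 0.090²] = +1.3 points. The test is non-significant at 5% while the interval lies above zero. For a single arm with 0/39, the two-sided 95% Clopper-Pearson upper limit is 1 − 0.025^(1/39) = 9.0%.

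**The case against.** The case on the other side is substantial in four respects.

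- **No safety claim is tested.** The study aim, hypothesis and primary aim concern pain and opioids. Safety as a purpose rests on one Background sentence, and the secondary aim speaks of looking at incidence, which is descriptive. No margin or power is claimed, so low power contradicts nothing in the plan. This stands, and it is why the remedy is estimation and not more patients. For scale, 80% power for 10% v 20% at two-sided 5% would need about 199 per arm.
- **Interpretation.** A reader might infer that a non-significant test will be reported as showing no difference, or as showing safety. The documents do not say so. They are silent on how such a result will be read, and that silence is what needs correcting.
- **Rates.** A reader might infer that a doubling of most harms would be missed at least 78% of the time. That figure needs a placebo rate of 10% or lower and a two-sided 5% test; for commoner events the miss rate falls to 64%, 50% and lower. The 1.3% to 6.2% figures in *Risk/Benefit Assessment* cannot supply the placebo rate, because they are reactions reported with Exparel.
- **Other safeguards.** Unblinded review continues through the trial, wound dehiscence is a named ground for termination, and proportions by arm will be shown. A harmful pattern would therefore not necessarily go unnoticed, and a reader could work out an interval from the counts. This protects participants but does not give the final report an estimate of excess risk.

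Nor is it true that equal counts always leave an excess of 10 points open: 0 v 0 gives ±9.0 points, although 2 v 2 gives ±12.3.

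**Conclusion.** The point holds as a gap in the analysis plan. Safety is a stated purpose, adverse events have no analysis entry, and the only comparative inference on them is a p-value. Under the plan's own test rule at two-sided 5% with 39 per arm, that p-value misses a doubling 95%, 78%, 64% and 50% of the time for placebo rates of 5%, 10%, 15% and 20%. The 2.5% level or 5% dropout makes it worse. These rates are assumptions, as is the expected-count threshold for switching to the exact test. The documents do not support the stronger conclusions that the trial is undersized for a safety claim it makes, or that it plans to treat non-significance as safety. The efficacy analyses, the sample size and trial conduct are unaffected.

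**What to change.** In *Statistical analysis*, add a paragraph for adverse events in place of relying on the chi-square test. It should cover:
- each event under *Adverse events will be recorded*;
- the neurologic signs under *Cardiac and Neurologic Monitoring*;
- nausea and vomiting;
- any serious adverse event.

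For each of these, report:
1. counts and proportions by arm;
2. the risk difference, Exparel minus placebo, with a two-sided 95% Newcombe or exact interval (name one in advance);
3. a two-sided 95% Clopper-Pearson interval for each arm's rate.

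State that a non-significant test will not be taken as evidence of safety. In the Background section, describe the safety aim as estimating event rates and their difference with this precision, for example an upper limit of 9.0% when none of 39 patients has the event.

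The cost is SAP wording and one more output per event, from data already collected. There are no extra patients or procedures. The intervals will be wide, so the safety statement will be less favourable than a row of non-significant p-values might look.

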### **Measurements/Data collection.**

#### Pain assessment:

The adult NVPS will be used to assess pain while patient is intubated in the ICU. This scale is used routinely in intubated and nonverbal critically ill patients in the Cardiovascular ICU (CVICU). The NVPS will be performed by a blinded care provider (e.g. nurse or nurse manager) who is trained on how to use the scale. Time 0 will be designated as the time the patient leaves the OR. The NVPS will be performed every 2 hrs for the first 4 hrs and then every 4 hrs following until the patient is extubated.

The numerical rating scale (NRS) ranging from 0 (no pain) to 10 (worst pain ever) will be used to assess pain

once the patient is extubated and alert. The scale will be administered every 4 hrs for the first 72 hrs post-op.

Cumulate pain scores at time points at 2, 4, 8, 12, 24, 36, 48, 60 and 72 hrs will be compared.

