#### Opioid requirements:

All narcotics will be converted to fentanyl equivalents (see Appendix VI) in order to calculate total morphine requirements for each interval. Cumulate morphine equivalents used at time intervals 2, 4, 8, 12, 24, 36, 48, 60 and 72 hours will be calculated.

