### **Data Analysis.**

#### Data Analysis

- Patient demographics/Pre-op characteristics:
  - Age, sex, race, Body surface area (BSA)/BMI
  - Co-morbid diseases: Diabetes mellitus, COPD, smoking, hypertension, coronary artery disease
  - Left ventricular ejection fraction (%)

- Creatinine (Cr), Cr clearance
- Functional status: New York Heart Association (NYHA) class, American Society of Anesthesiologists (ASA) classification
- Intra-operative characteristics:
  - Operation type: CABG (on/off bypass), AVR, MV repair/replacement, Maze, Other (i.e. TV repair/replacement, ASD closure)
  - Internal mammary artery (IMA) harvested (one or two)
  - Cardiopulmonary bypass time (min)
  - Aortic cross-clamp time (min)
  - Intraoperative fentanyl ( $\mu\text{g}$ ), intraoperative versed (mg)
- Pain assessment:
  - Calculate mean area under the curve (AUC) for adult NVPS scores over the time intervals “0-2”, “0-4”, “0-8” and “0-12” hours.
  - Calculate mean AUC for NRS scores over the time intervals “0-12”, “0-24”, “0-36”, “0-48”, “0-60” and “0-72” hours.
- Opioid requirement:
  - Calculate mean cumulative fentanyl equivalent use for time intervals “0-2”, “0-4”, “0-8”, “0-12”, “0-24”, “0-36”, “0-48”, “0-60” and “0-72” hours.
  - Use of breakthrough pain medication (e.g. Toradol or Tramadol)
- ICU length of stay:
  - Calculate mean lengths of stay (hours) for placebo and Exparel® groups.
- Hospital length of stay:
  - Calculate mean lengths of stay (days) for placebo and Exparel® groups.
- Time to extubation:
  - Calculate mean time to extubation (hours) for placebo and Exparel® groups.
- Time to return of bowel function:
  - Calculate mean time to return of bowel function for placebo and Exparel® groups.
- Splinting
  - Mean change in IC from pre-operative to POD #1-2 in both treatment arms.
- Assessment of blind
  - Calculate the percentage of correctly guessed treatment assignments.

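### The 2.5% level is not tied to one deciding test per primary outcome: no NRS window is designated, 0–24 h has no deciding status for opioid use, and no analysis method is named as decisive

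*Combined protocol and SAP*

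**What the plan says.** **Level.** Section II (Number of subjects) and Section III (Statistical analysis) give the same single reason for the level: "Since there are two primary outcomes, a type I error of 2.5% will be used". Tests are two-sided.

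**Power.** For pain, the plan claims "86% power to detect a 30% decrease in mean NRS scores at the 2.5% level of type I error (two-sided"), without naming a window or summary measure. For opioids it claims "98% power to detect a 30% decrease in total opioid consumption over the first 24 hours post-operatively".

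**Pain windows.** Under Pain assessment: "Cumulate pain scores at time points at 2, 4, 8, 12, 24, 36, 48, 60 and 72 hrs will be compared". Under Data Analysis: "Calculate mean AUC for NRS scores over the time intervals" 0–12, 0–24, 0–36, 0–48, 0–60 and 0–72 h. There are four further windows for the NVPS.

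**Opioid windows.** Under Opioid requirements: "Cumulate morphine equivalents used at time intervals 2, 4, 8, 12, 24, 36, 48, 60 and 72 hours will be calculated". Under Data Analysis: "Calculate mean cumulative fentanyl equivalent use for time intervals" that run from 0–2 h to 0–72 h, nine in all, with 0–24 h among them. No pain or opioid window is marked primary.

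**Methods.** Statistical analysis names a t-test or Wilcoxon test (chosen by distribution) and a covariate-adjusted linear model for NRS, with covariates not listed. It adds "Regression analysis will also be applied to opioid requirements", and then a Tobit model for opioid use. Mixed models and GEE/WGEE are an optional refinement of the NRS AUC analysis. If those two disagree, GEE/WGEE is preferred.

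**Success rule.** The primary aim joins better analgesia and lower opioid use with the word and. No rule says whether one significant outcome is enough.

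**The concern.** A two-way split of alpha pays for two tests. Here it is attached to two outcome domains, each of which can be tested over several windows and by several models. The reader cannot tell which NRS p-value is to be held against 2.5%, nor which comparison has 86% power. For opioids the power statement implies an answer, but the analysis text never confirms it.

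The choice of window matters on the plan's own account. The Background reports that the ropivacaine block's advantage was greatest in the first 12 hours and then shrank, and that the liposomal product's benefit after hemorrhoidectomy was more substantial from 12 to 72 hours. A 0–12 h AUC and a 0–72 h AUC therefore ask different questions and could give different answers. If the window or model is settled after group data have been seen, the 2.5% level no longer gives the protection it was set to give.

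**Working it through.** **1. Reproduce the stated power as single tests.** Inputs from Number of subjects: NRS mean 53.2, SD 24.1; opioid mean 23.2 mg, SD 8.3 mg; 30% reduction; treated SD scaled by 0.7; 39 per arm; two-sided 0.025 (z = 2.241).

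Power = Φ(Δ / √[(SD₁² + SD₂²)/n] − 2.241)

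- NRS: Δ = 0.3 × 53.2 = 15.96; SDs 24.1 and 16.87; SE = √(865.4/39) = 4.71; Φ(3.388 − 2.241) = 87.4% (86.2% with the t distribution).
- Opioid: Δ = 6.96; SDs 8.3 and 5.81; SE = √(102.6/39) = 1.622; Φ(4.290 − 2.241) = 98.0% (97.6% with t).
- At 37 evaluable per arm (37/0.95 rounds up to 39): NRS 84.2% (t) or 85.5% (normal); opioid 96.9% or 97.4%.

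The stated 86% and 98% are sound, but each describes one test.

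**2. What the split buys.** With one fixed test per outcome and success on either, the error is at most 0.025 + 0.025 = 5%; under independence it is 1 − 0.975² = 4.9%.

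**3. What happens if any listed window may be claimed.** Independent tests would give 1 − 0.975⁶ = 14.1% (six NRS windows) and 1 − 0.975⁹ = 20.4% (nine opioid windows). These overstate the problem, because the windows are nested. The documents give no correlations, so this step is a null simulation on assumed ones: 37 per arm, 20,000 trials per setting, t-tests at 0.025, NRS every 4 h with trapezoid AUC, opioid use in 2 h bins. Assumed inputs are the within-patient correlation (ICC), the 4 h autocorrelation (AR) and a correlation of 0.2 between patients' pain and opioid levels.

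| ICC, AR | any NRS | any opioid | any NRS, or opioid 0–24 h | any NRS or any opioid | both outcomes, any window |
|---|---|---|---|---|---|
| 0.2, 0.5 | 6.1% | 8.4% | 8.6% | 14.0% | 0.5% |
| 0.3, 0.5 | 5.5% | 8.2% | 8.1% | 13.2% | 0.5% |
| 0.5, 0.5 | 5.1% | 6.2% | 7.4% | 10.9% | 0.4% |
| 0.5, 0.8 | 4.8% | 5.5% | 7.0% | 9.9% | 0.3% |
| 0.7, 0.8 | 4.3% | 4.4% | 6.4% | 8.5% | 0.2% |

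With one fixed window per outcome, the either-outcome rate in the same simulation is 4.4–5.2%. Varying the cross-outcome correlation from 0 to 0.5 gives 6.3–8.6% for any NRS window or opioid 0–24 h, and 8.5–14.0% with all windows open. At the extremes, zero within-patient correlation gives 10.4% and 19.6%; ICC 0.9 with AR 0.8 gives 5.6% and 6.9%.

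**4. Direction.** These are two-sided rejections. Counting only those that favour the study drug, the rate for any NRS window or opioid 0–24 h is about 3.3–4.2%, against a nominal 2.5%.

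**5. If both outcomes are required.** The global-null rate is 0.1–0.7%. If opioid use truly falls as planned and NRS does not change, an NRS rejection in any window occurs in 3.4–5.9% of trials (two-sided), against 2.0–2.7% with one fixed window. In the benefit direction the rates are about 2.0–3.1% against 1.2%.

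**6. Does the NRS power carry over to a chosen window?** It depends on SD/mean, which is 24.1/53.2 = 0.453 in the plan. At 37 per arm (t distribution), a ratio of 0.40 gives 92%, 0.50 gives 76% and 0.60 gives 58%. These ratios are illustrative; the plan gives none by window.

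**The case against.** **A reader may infer 0–24 h for both outcomes.** Both planning inputs come from the cited ropivacaine trial, which by the Background's account observed patients for about 24 hours. For opioids this inference is fair. For NRS it only points to a horizon of 24 h at most: the sentence names no window, 0–12 h and 0–24 h both fit, and a mean of 53.2 cannot be a single score on a 0–10 scale, so the summary it represents is unknown.

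**The plan nowhere says that any significant window counts as success.** That is correct. Most windows are only to be calculated, although the pain time points are to be compared. The and in the primary aim could mean that both outcomes are required, in which case the overall error is very small. The 6–14% range is therefore what the wording leaves open, not what the plan prescribes.

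**Stronger readings that the documents do not support.**
- A reader might infer that 0–24 h drops out of the opioid analysis. It is listed; only its deciding status is missing.
- A reader might infer from the Self-audit section that investigators compare pain and opioid data between letter-coded groups at 39 patients. The explicit list of pain scores and opioid use belongs to the audit after the first patient, and no between-group comparison is scheduled at 39.
- A reader might take the two-sided rates as rates of false success. Success means benefit, and in that direction they are about half.

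**The magnitudes are fragile.** Other assumed correlation structures give 3.9–7.8% for any NRS window and 6.0–10.0% for any opioid window. The simulation starts NRS at time 0, whereas the plan starts it after extubation. This limits the precision of the figures but does not touch the missing designation.

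**Conclusion.** The point stands. The plan states a level and a reason for it, but supplies no single window and method per outcome to which the level applies. The gap is complete for NRS. For opioids it is a matter of confirming what the power section implies. Confidence is high on the missing designation and only moderate on its size.

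On the either-outcome, any-window reading, the two-sided overall error is about 6–9% with opioid use fixed at 0–24 h and about 8–14% with all windows open, instead of about 5%. On the both-outcomes reading, the overall null rate is below 1%, but the NRS result still carries about 4–6% two-sided error instead of 2.5%. All of these rest on assumed correlations. The choice among models and the NVPS windows is not counted. Because the designation determines what a positive trial means, it should be settled before analysis.

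**What to change.** Before any between-group look at efficacy data, including any by letter code:

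- **Opioid use:** designate cumulative use over 0–24 h, matching the power statement, and one analysis method.
- **NRS:** designate one AUC window, chosen by the sponsor, and one analysis method. Confirm or restate the 86% power for that window.
- **Success rule:** state whether success needs either outcome or both. If both, state the joint power; at 37 per arm it is about 0.842 × 0.969 = 82% if the outcomes are independent (81–83% in simulation).
- **Level:** apply 2.5% to those two tests only. Label every other window and model secondary or supportive.

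For the analysis section this is a change of wording. The cost is the freedom to claim other windows, and possibly a lower stated NRS power if the chosen window is more variable than assumed. Keeping all windows open under a Bonferroni correction would cost more: 0.025/6 cuts NRS power at 37 per arm to about 63–67%, and the correction is conservative for nested windows.
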